Version No. 1.0, Version date 07 October 2019

A Phase II, Single-center, Single-arm Clinical Trial on the Efficacy and Safety of Anti-PD-1 antibody (IBI308) Combined with Anlotinib for the Treatment of Recurrent or Advanced Endometrial Cancer

Principal investigator: Chief Director [name]

Study site: Department of Gynecology, Sun Yat-sen University Cancer Center

Version: 1.0

Version date: 7 October 2019

Version No. 1.0, Version date 07 October 2019

Table of Contents

Protocol Synopsis.....	2
List of Abbreviations.....	6
Study Visit Schedule.....	8
Study Background and Theoretical Basis.....	11
Study Objectives.....	16
Study Design.....	17
Trial Population.....	17
Investigational Drug and Treatment Design.....	20
Dose Modifications.....	22
Concomitant Treatment.....	30
Trial Procedure.....	31
Efficacy Evaluation.....	33
Statistical Analysis.....	39
Ethical Standards.....	40
Study Management.....	14
References.....	41
Appendix 1. ECOG Scale of Performance Status (ECOG PS).....	43
Appendix 2: Response Evaluation Criteria in Solid Tumors (RECIST) Version 1.1 (excerpts)	44

Protocol Synopsis

Study Title	A Phase II Single-center, Single-arm Clinical Trial on the Efficacy and Safety of Anti-PD-1 antibody (IBI308) Combined with Anlotinib for Recurrent or Advanced Endometrial Cancer
Study objective	To examine the efficacy and safety of anti-PD-1 monoclonal antibody (IBI308) combined with anlotinib for recurrent or advanced endometrial cancer.
Study design	A non-randomized, single-arm, open-label, phase II clinical trial
Principal investigator	[name]
Inclusion criteria	
 1. Women aged > 18 years; 2. Histologically confirmed endometrial cancer; 3. Recurrent or advanced endometrial cancer with at least one treatment with systemic platinum-based chemotherapy; 
 • Low probability of cure for recurrent endometrial cancer with surgery and/or radiotherapy and failure of at least one systemic platinum-based chemotherapy after recurrence. • Newly diagnosed advanced endometrial cancer persisting after standard treatment with surgery ± radiochemotherapy and at least one systemic platinum-based chemotherapy. 4. Objectively measurable lesions based on Response Evaluation Criteria In Solid Tumors (RECIST 1.1) and at least one target lesion; 
 • In principle, lesions in the field of previous radiotherapy are considered non-target unless there is radiological evidence of progression or a biopsy with progression within 90 days after radiotherapy. 5. Eastern Cooperative Oncology Group (ECOG) score of 0–2; 6. Expected survival >3 months; 7. Major organ function fulfilling the following criteria (correction of the following parameters and supportive treatment are permitted one week before enrollment);

	
 • Absolute neutrophil count $\geq 1.5 \times 10^9/L$, platelet count $\geq 70 \times 10^9/L$, hemoglobin ≥ 80 g/L • Alanine transaminase (ALT) and aspartate transaminase (AST) ≤ 2.5 times upper limit of normal (ULN) (< 5 times for patients with liver metastases) and total bilirubin ≤ 1.5 times ULN • Serum creatinine ≤ 1.5 times ULN • International normalized ratio (INR) < 1.5 times ULN • Proteinuria $\leq (+)$ • Thyroid-stimulating hormone (TSH) ≤ 1 time ULN (measure FT3 and FT4 if TSH abnormal; subjects with normal FT3 and FT4 can be enrolled) 
8. Voluntarily signed informed consent form.

Exclusion criteria	
 1. Presence of carcinosarcoma in pathology specimen (including malignant mixed Müllerian tumor, uterine leiomyosarcoma, and endometrial stromal sarcoma); 2. Received other antineoplastic drugs 4 weeks before the first dose; 3. Underwent major surgery in the past 28 days or expected to undergo major surgery during the study period; 4. Received radiotherapy 21 days before drug administration (palliative radiotherapy within 2 weeks for subjects with bone metastases); 5. Prior therapy with anti-PD-1 antibody; 6. Grade > 1 unresolvable and persistent adverse reaction caused by previous treatment (except for alopecia and grade > 2 neurotoxicity); 7. Patients currently on immunosuppressants or systemic steroid treatment (dose > 10 mg/day prednisone or another equivalent steroid) and still on immunosuppressive treatment 2 weeks before enrollment. 8. Other malignant tumors in the last 5 years (except for adequately treated in situ malignant tumors such as breast cancer, bladder carcinoma, cervical carcinoma in situ, basal cell carcinoma, or squamous cell carcinoma of the skin); 9. Psychotropic substance abuse that the subject is unable to discontinue or subjects with mental disorders; 10. Central nervous system disorders including uncontrolled epilepsy and symptomatic brain metastases;

	
 11. A digestive disorder that affects drug absorption (such as atrophic gastritis). 12. Patients with an active ulcer, intestinal perforation, or unresolved intestinal obstruction and patients with digestive tract perforation 28 days before enrollment; 13. Uncontrolled hypertension (blood pressure >140/90 mmHg) after adequate conventional treatment; 14. Severe cardiovascular disease: unstable angina, myocardial infarction, class III–IV heart failure (NYHA criteria), and grade 2 and above peripheral vascular disorder 6 months before enrollment; 15. Severe arrhythmia requiring drug control and a clinically significant prolonged QT interval (>470 ms); 16. Active bleeding or a bleeding tendency; 17. Arterial/venous thrombosis 6 months before enrollment, such as cerebrovascular events (including stroke, transient ischemic attacks, subarachnoid hemorrhage), deep vein thrombosis, and pulmonary embolism; 18. Active infections, such as HIV/AIDS or other severe infections; 19. Any active autoimmune disease or history of autoimmune disease (including but not limited to autoimmune hepatitis, interstitial pneumonia, hepatitis, enteritis, nephritis, hyperthyroidism, hypophysitis, vasculitis, uveitis) or patients who require systemic steroid and/or immunosuppressant treatment (such as asthma requiring steroid-bronchodilator treatment); 20. Received a live vaccine within 30 days before the first dose; 21. Known allergy to any of the study drugs; 22. Women of child-bearing age must have a negative pregnancy test and follow strict contraceptive measures during the trial; 23. Patients deemed unsuitable for enrollment by the investigator.
Treatment withdrawal criteria	
 1. Subject withdraws informed consent; 2. Radiologic examination shows disease progression; 
 • Since pseudoprogression occurs with PD-1, confirmation should be performed 4–6 weeks after the first disease progression result except for

	
significant clinically rapid progression or patients with an unstable general condition.
 
 3. The cumulative treatment period with anti-PD-1 antibody reaches 2 years; 4. Radiological examination shows that drug discontinuation can be considered for CR subjects who have completed 6 cycles of drug administration. 5. Intolerable toxicity; 6. Poor compliance; 7. Loss to follow-up. 8. The investigator considers that the subject must withdraw from the study.
Treatment regimen	
IBI308: Product name (sintilimab), 200 mg intravenous infusion, qd, d1, q3w,
 
Anlotinib: 12 mg/tablet, one tablet daily, orally half an hour before breakfast, d1–d14, and 1 treatment cycle lasting 3 weeks. The patient will take the study drug until protocol-stipulated treatment withdrawal criteria are fulfilled.

Sample size calculation Statistical methods	
Simon's 2-stage design was used for sample size estimation. An alpha of 0.05 (one-tailed), a beta of 0.2, and a power of 0.8 were used. Based on existing literature, the objective response rate (ORR) of anti-PD-1 monoclonal antibody monotherapy in advanced or PD-L1-positive recurrent endometrial carcinoma after failure of first-line chemotherapy is 13%.
 
Assuming that IBI308 combined with anlotinib can increase efficacy by 26%, the ORR is 39%. At least 23 patients are needed. Seven patients will be enrolled in stage 1. When the number of valid patients < 2, combination therapy is considered not superior to monotherapy, and this trial will be terminated. Otherwise, 16 subjects will be enrolled in stage 2. The trial is rejected if there are ≤5 patients with ORR in the two stages. Percentages, χ^2 test, and analysis of variance are used to analyze efficacy. Descriptive methods and percentages will be used for safety analysis.

Efficacy evaluation	
RECIST (v1.1) and irRECIST criteria are used for radiologic tumor evaluation after the 2nd treatment cycle (\pm 7 days) and after week 4 (\pm 7 days) after the start of dosing. Subsequently, radiologic tumor evaluation will be performed once every 3 treatment cycles (\pm 7 days) until the 10th cycle. After the 10th cycle, radiologic tumor evaluation will be performed every 4

	treatment cycles (\pm 7 days). Additional examinations can be performed if clinical progression occurs.
Study markers	
Primary study markers
 
 • Objective response rate (ORR) 
Secondary study markers
 
 • Duration of response (DOR): • Disease control rate (DCR) • Time to objective response (TTR) • Clinical benefite rate (CBR) • Progression-free survival (PFS) • Probability of PFS > 6 months and 12 months • Overall survival (OS) • Evaluation of the safety and tolerability of IBI308 combined with anlotinib
Version number	v1

List of abbreviations

AE	Adverse Event
ALT	Alanine aminotransferase
AST	Aspartate aminotransferase
CR	Complete Response
Cr	Creatinine
CRF	Case Report Form
DCR	Disease control rate
DO	Duration of response
ECG	Electrocardiogram

ECOG	Eastern Cooperative Oncology Group
FDA	Food and Drug Administration
GCP	Good Clinical Practice
HBV	Hepatitis B virus
HCV	Hepatitis C virus
HIV	Human Immunodeficiency Virus
ICF	Informed Consent Form
irAE	Immune-related Adverse Event
irRECIST	Immune-related Response Evaluation Criteria in Solid Tumors
NYHA	New York Heart Association
ORR	Objective response rate
OS	Overall Survival
PD-1	Programmed cell death 1
PFS	Progression Free Survival
PR ^{RECIST}	Partial Response
RECIST	Response evaluation criteria in solid tumors
SAE	Severe Adverse Event
SD	Stable Disease
TBIL	Total bilirubin
TMB	Tumor mutation burden
TTR	Time to response
ULN	Upper limit of normal

Table 1. Study Visit Schedule

Period	Screening period	Treatment period						Maintenance therapy	Safety visit	Survival visit
Time window	Day-28 before dosing	Cycle 1			Subsequent cycles			One treatment cycle of 21 days (\pm 3 days)	30 days after the last dose (\pm 3 days)	Once every 3 months (\pm 3 days)
		C1/d1	C1/d8/d15	C1/d21	C2-x/d1	C2-x/d8	C2-x/d15			
		-3	\pm 3	\pm 3	-3	\pm 3	\pm 3			
Clinical study information										
Informed consent form ¹	X									
Inclusion/exclusion criteria	X									
Demographics/past medical history	X									
Concomitant medications	X				X					

Vital signs ²	X				X					
Weight/height and physical examination ³	X				X					
Laboratory tests										
Routine blood tests ⁴		X	X		X	X	X	X	X	
Blood chemistry ⁵		X			X			X	X	
Routine urine tests ⁶		X			X			X	X	
Routine Stool test ⁷		X			X			X	X	
Coagulation function ⁸		X			X					
Thyroid function test ⁹	x				d1 of Cycle 2 and d1 of every 3 subsequent cycles			X		
Tumor markers	X				X			X		
Hepatitis B, hepatitis C test ¹⁰	X				If positive, hepatitis B DNA and hepatitis C RNA will be measured on d1 ± 7d in every 2 cycles					
HIV test ¹⁰	X									
Pregnancy test ¹¹	X									

12-lead electrocardiogram		X			X			X	X	
Clinical evaluation examination										
ECOG scoring	X				X					
Evaluation of adverse events ¹²	From the signing of the informed consent form to 30 days after the last dose									
Quality of life questionnaire ¹³		X			X ⁸				X	
Administration of investigational product										
IBI308 administration		X			X					
Anlotinib administration	Administration is recorded daily on d1–d14 of every treatment cycle									
Efficacy evaluation										
Radiologic tumor evaluation ¹⁴	X	Evaluation is performed once after the 2nd treatment cycle (C3) and once after the 4th treatment cycle (C5). Subsequently, an evaluation will be performed once after the 7th cycle (C8) and once after the 10th cycle (C11). After the 10th cycle, an evaluation will be performed once every 4 treatment cycles, and the time window for radiological evaluation is ± 7 days.								
Follow-up after treatment has ended										

Progressive disease	Radiologic evaluation is performed every 3 months after the last dose until disease progression						
Biomarker exploration							
Biomarker blood sampling/sample collection	X						

1. The informed consent form should be signed by subjects before any procedures outlined in the protocol.
2. Vital signs include body temperature, pulse, respiratory rate, and blood pressure.
3. Height is only measured during the screening period. Weight is measured before every dose, except for physical examination during the screening period; physical examination abnormalities during the trial only need to be recorded in the CRF.
4. Routine blood tests include RBC, HGB, HCT, WBC, PLT, and white blood cell categories [LYM, ANC, MONO, EOS, BASO].
5. Blood chemistry includes liver function tests [TBIL, ALT, AST, γ -GT, ALP, ALB, TP, LDH], renal function tests [UREA, Cr], blood electrolytes [Na, K, Cl, Mg], amylase, lipase, blood lipids [total cholesterol (CHO), triglycerides (TG), high-density lipoprotein cholesterol, low-density lipoprotein cholesterol], and fasting blood glucose.
6. Routine urine tests include UWBC, UPRO, URBC, UGLU. Any subjects with $\geq 2+$ proteinuria in routine urine tests must undergo 24-hour urine protein quantification during the screening period.
7. Routine stool test should include stool routine.
8. Coagulation function tests should include PT, APTT, INR, D-dimer, and fibrin degradation products.
9. Thyroid function test should include TSH, FT3, and FT4. Only TSH is tested from Cycle 2 onwards and once every 3 cycles if there are no abnormalities.
10. HIV and HCV antibody tests and 5-item hepatitis B (HBsAg, HBsAb, HBcAb, HBeAg, and HBeAb) tests must be completed within 28 days before the first dose. HCV antibodies are tested during the screening visit. HCV-RNA load will be measured for HCV antibody-positive subjects once every 3 weeks (21 ± 3

days) starting from the first dose or earlier when clinically indicated. 5-Item hepatitis B tests are performed during the screening visit. For HBsAg and/or HBcAb-positive subjects, HBV-DNA load will be measured once every 3 weeks (21 ± 3 days) starting from the first dose or earlier when clinically indicated.

11. Women of child-bearing age should undergo a urine or blood pregnancy test within 3 days before the first dose during the screening period. A serum pregnancy test will be performed if the urine pregnancy test cannot determine pregnancy; the serum pregnancy test result will prevail.

12. AE and laboratory test safety assessment will be based on CTCEA v4.03. The definitions, documentation, correlation judgment, severity judgment, reporting deadline, and management of AEs and SAEs will be based on the descriptions in the protocol.

13. EORTC QLQ-EN24 will be used as the quality of life questionnaire, and the evaluation will be performed on the day of the first dose (before dosing) and at every radiologic evaluation. The quality of life questionnaire must be performed at the same time if unscheduled radiologic evaluations are performed.

14. Tumor evaluation includes irRECIST and RECIST 1.1. Radiologic tumor examinations usually include contrast-enhanced CT or MRI. The examination sites must include the chest, abdomen, and pelvic cavity. Enhanced cranial MRI scan must be performed at baseline for patients with suspected signs or symptoms of central nervous system metastases. The type of radiologic examinations received by a subject during the study period should be the same. Baseline evaluation will be performed within 28 days before the first dose. Radiologic tumor evaluation will be performed once in Week 2 (± 7 days) and Week 4 (± 7 days) after the start of dosing. Subsequently, radiologic tumor evaluation will be performed once every 3 treatment cycles (± 7 days) until the 10th cycle. After the 10th cycle, radiologic tumor evaluation will be performed once every 4 treatment cycles (± 7 days). After the investigator has evaluated the first radiologic progression based on irRECIST, current treatment can be continued if the patient has stable clinical disease without significant progression, and radiologic evaluation will be performed after 4–6 weeks for confirmation (based on irRECIST). If progression is not confirmed, study treatment can be continued.

1. Study Background and Theoretical Basis

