8.5 Survival visit

An outpatient or telephone follow-up will be performed 1 month after the last dose for every subject; adverse events and concomitant medications within 1 month of the end of treatment will be recorded. Subsequent follow-up on overall evaluation data will be performed until disease progression or new antineoplastic treatment starts. Subsequent antineoplastic treatment and its start date will be recorded, and survival follow-up will be performed.

If the subject withdraws from the study due to toxicity symptoms, withdrawal of informed consent, and disease progression, it will be considered the end of treatment. The reason for treatment discontinuation, the treatment end date, and the withdrawal date will be recorded. At the end of treatment, adverse reactions and concomitant treatments within 30 days after the last dose of the investigational drug will be collected.

9. Efficacy Evaluation

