During the screening, the first tumor radiologic examination must be performed within 28 days before treatment. Evaluation is performed once after the 2nd treatment cycle (C3) and once after the 4th treatment cycle (C5). Subsequently, an evaluation will be performed once after the 7th cycle (C8) and once after the 10th cycle (C11). After the 10th cycle, an evaluation will be performed once every 4 treatment cycles, and the time window for radiologic evaluation is ± 7 days. Additional examinations can be performed if clinical progression occurs. The investigator will simultaneously evaluate RECIST1.1 and record the results, but this will not be used as a reference for treatment. After the investigator has completed the first radiologic evaluation of disease progression based on irRECIST, current treatment can be continued if the patient has stable clinical disease; radiologic evaluation will be performed after 4–6 weeks for confirmation (based on irRECIST). Treatment will be discontinued if progression is confirmed. If progression is not confirmed, study treatment can be continued until PD is confirmed by radiologic evaluation. An unscheduled radiologic evaluation can be performed at any time if the patient suffers unstable clinical disease during the study.

The definition of unstable clinical disease is as follows:

- Development of clinically significant signs and symptoms suggesting disease progression (including worsening laboratory test values)
- Decrease in ECOG PS score

- Rapid disease progression
- Tumor progression at important anatomical sites that requires other emergency medical interventions (such as spinal cord compression)

Patients who require treatment discontinuation for reasons other than disease progression shown in the radiologic evaluation should undergo radiologic evaluation at the end of treatment and after that at scheduled time points stipulated in the protocol until any one of the following events occurs: start of new antineoplastic therapy, objective disease progression, withdrawal of informed consent by the subject, loss to follow-up, or death.

Baseline cranial CT/MRI examination should be performed before starting study treatment in subjects with known or suspected brain metastases at screening. During the study period, cranial CT/MRI evaluation should be performed on these subjects, and brain metastases are considered non-target lesions for evaluation.

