If the investigator cannot determine whether disease progression has occurred, particularly for non-target lesions and new lesions, the subject can continue treatment until clinical symptoms occur or the next scheduled evaluation where radiologic evaluation is repeated. If disease progression is confirmed, then the date of progression should be the initial date of discovery. For subjects who discontinue treatment due to treatment completion or reasons other than objective disease progression, radiologic tumor evaluation should be performed once at treatment completion/discontinuation. A subsequent radiologic evaluation should be performed according to a protocol-stipulated radiologic examination schedule until one of the following situations occurs: start of new antineoplastic therapy, objective disease progression, death, or end of the study, whichever comes first.

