9.5. Overall response determination

Overall evaluation of disease response involves all parameters listed in the following table. The best overall response refers to the best response recorded from the start of treatment to disease progression/recurrence (the lowest measurement recorded since the start of treatment is used as a reference for determining tumor worsening). The best response of the patient is determined by the measurement method and confirmation criteria.

Table 8. Timepoint efficacy determination based on irRECIST criteria.

Overall efficacy evaluation:

Target lesion	Non-target lesion	New lesion	Overall response
CR	CR	None	CR
CR	Non-CR/SD	None	PR
PR	PD absent	None	PR
SD	PD absent	None	SD
PD*	Any response	Present or absent	PD
Any response	PD	Present or absent	PD
Any response	Any response	Present	PD

*Reconfirmation according to irRECIST criteria is required

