9.4 Endpoint criteria

Primary endpoint:

Objective response rate (ORR): Defined as the proportion of patients whose tumor volume shrunk to the pre-stipulated value and maintained for more than 4 weeks; i.e., ORR = CR +

PR. The internationally accepted RECIST 1.1 and irRECIST criteria are used for solid tumor evaluation. ORR is used as the primary endpoint for the clinical trial.

Secondary endpoints:

Duration of response (DoR): Time from first evaluation of CR or PR until evaluation of PD or death from any cause. For patients who did not experience PD or death, the last radiologic tumor evaluation date will be the censor date.

Disease control rate (DCR): The proportion of subjects with CR, PR, or SD based on RECIST 1.1 criteria in the analysis set.

Time to response (TTR): Time from start of treatment to first objective response (CR or PR). For patients that did not experience CR or PR, the last radiologic tumor evaluation date will be the censor date.

Progression-free survival (PFS): Defined as time from subject enrollment to tumor progression or death.

Overall survival (OS): Time from start of treatment to death. If the subject is still alive at the end of the study, the “last known date of subject survival” will be the censor date.

12-month OS rate: The proportion of patients that are alive at month 12 after starting treatment.

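### The protocol gives two incompatible stopping rules for post-treatment scans, and the best-response window does not end at new anticancer therapy, so a response to a later drug can count in the primary ORR

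*Protocol*

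**What the plan says.** **When post-treatment imaging stops**

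- Table 1 (Study Visit Schedule), follow-up after treatment has ended: "Radiologic evaluation is performed every 3 months after the last dose until disease progression". New therapy is not named.
- Section 8.5 (Survival visit): "Subsequent follow-up on overall evaluation data will be performed until disease progression or new antineoplastic treatment starts". The start date of subsequent antineoplastic treatment is to be recorded.
- Section 9.1, for patients who stop for reasons other than radiologic progression, continues imaging at the scheduled time points up to the first of: "start of new antineoplastic therapy, objective disease progression, withdrawal of informed consent by the subject, loss to follow-up, or death".
- Section 9.1, second statement, follows the protocol's imaging schedule up to: "start of new antineoplastic therapy, objective disease progression, death, or end of the study, whichever comes first".

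**Endpoint definitions**

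- Section 9.5 (Overall response determination): "The best overall response refers to the best response recorded from the start of treatment to disease progression/recurrence".
- Section 9.4, PFS: "Defined as time from subject enrollment to tumor progression or death". No censoring rule is given.
- Section 9.4, DoR: from first CR or PR to PD or death from any cause. Patients with neither are censored at their last radiologic evaluation.

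None of these three definitions mentions new anticancer therapy, and section 11.2 gives no rule for it.

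**Decision rule (section 3.1)**

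The design is a Simon two-stage design with null ORR 13% and target 39%. Seven patients enter stage 1, and the trial stops if there is at most 1 response. Sixteen more enter stage 2, and the treatment is rejected if there are at most 5 responses in the 23.

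**The concern.** Take a patient who stops the study drugs for toxicity, has not progressed, and starts another anticancer drug. Table 1 keeps this patient in 3-monthly imaging. Sections 8.5 and 9.1 end imaging at the switch. A site cannot do both, and the protocol does not say which text governs.

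The choice matters because of the best-response window. It runs from start of treatment to progression or recurrence and has no other end. If scans continue after the switch, a CR or PR produced by the next drug before progression meets the definition and counts in the endpoint that decides the trial.

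Such patients are foreseeable. Section 4.4 withdraws patients for serious adverse events, intolerable toxicity, other complications and poor compliance. The synopsis adds stopping in CR and at 2 years. Sections 8.4 and 8.5 expect subsequent therapy to occur. Section 3.1 keeps all enrolled subjects in the efficacy analysis.

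**Working it through.** **1. The texts side by side, for a patient who stops without progression and then switches**

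| Question | Table 1 followed | 8.5 / 9.1 followed |
|---|---|---|
| Protocol scans after the switch? | Yes, until progression | No |
| Can a later CR/PR enter best response (9.5)? | Yes, if before progression | No, unless unscheduled scans are used |
| DoR with no PD and no death | Censored at the last scan, possibly post-switch | Censored at the last pre-switch scan |
| Death after the switch, no PD recorded | PFS/DoR event at death, although PD may be seen first | PFS/DoR event at death; earlier PD is not looked for |

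The ORR problem belongs to the first column. The second column leaves only the late-death issue for PFS and DoR. For a given patient these are alternatives.

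**2. Imaging interval**

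Table 1 says every 3 months. Section 9.1 refers to the protocol schedule, which is after cycles 2, 4, 7 and 10 and then every 4 cycles. Four 3-week cycles are 12 weeks, close to 3 months, so the interval differs materially only for patients who stop early.

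**3. Reproducing the design**

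With response probability p, the chance of passing is

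P(pass) = Σ over x = 2…7 of Bin(x; 7, p) × P[Bin(16, p) ≥ 6 − x].

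At p = 0.13:

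- x = 2: 0.17689 × 0.14484 = 0.02562
- x = 3: 0.04405 × 0.34611 = 0.01525
- x = 4: 0.00658 × 0.63473 = 0.00418
- x = 5: 0.00059 × 0.89228 = 0.00053
- x = 6 and 7 together: 0.00003

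The sum is 0.0456. At p = 0.39 the same formula gives 0.8003. The stated one-sided alpha of 0.05 and power of 0.80 are met, and N = 23 reproduces. The design itself is not in question.

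**4. Illustration if post-switch responses are counted**

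The documents give no rate of switching before progression, so it is assumed. Let f be the share of study-drug non-responders who switch before progression, and q the share of those who then respond. For q, the range 4–27% is borrowed from section 1.3 (second-line single-agent chemotherapy). The effective response probability at a true 13% is

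p* = 0.13 + 0.87 × f × q,

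and the expected number of extra counted responses in 23 patients is 23 × 0.87 × f × q.

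| f | q | p* | Extra responses in 23 | P(pass) |
|---|---|---|---|---|
| 0 | – | 0.130 | 0 | 4.6% |
| 10% | 4% | 0.133 | 0.08 | 5.1% |
| 20% | 15% | 0.156 | 0.60 | 9.3% |
| 30% | 27% | 0.200 | 1.62 | 21.6% |

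The model is simple and probably generous. It lets a later response count towards the stage 1 decision whenever it occurs. It also ignores that a PR needs a 30% fall from the original study baseline, held for 4 weeks (sections 9.3 and 9.4), before any PD.

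**The case against.** The strongest reply is that one schedule-table row stands against three body-text statements that agree with one another. If the body text governs, protocol imaging ends at the switch, no later response is generated and ORR is clean. Section 4.4 also makes simultaneous use of other antineoplastic drugs a withdrawal criterion and requires a last evaluation before withdrawal. The per-protocol set in 11.1 excludes users of prohibited drugs and is analysed alongside the full set. This narrows the problem but does not close it. The protocol never says that body text overrides Table 1. The prohibition in 7.2 applies to the treatment period. Withdrawal from treatment does not end the best-response window, and section 9.1 allows unscheduled scans.

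A reader might infer that the effects of later therapy are in fact credited to sintilimab plus anlotinib, with ORR, PFS and DoR all inflated. The documents do not support that. The ORR effect is conditional on Table 1 or unscheduled scans. Under 8.5 and 9.1, DoR without PD or death is already censored before the switch. The ORR effect and the loss of progression through stopped imaging come from different scan rules and do not add up in one patient.

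A reader might also infer that PFS and DoR should be censored at new therapy as the main rule. Counting deaths regardless of later therapy is a recognised choice. Censoring patients who switch for toxicity or decline may be informative and can itself inflate PFS. Such detail is also commonly left to an SAP, which is not at hand. That objection stands.

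The objection to the size also stands in part. No passage gives a switching rate. The 4–27% comes from an earlier treatment setting than that of patients who have stopped the study combination. The top of the range needs both extremes at once, and the bottom is negligible.

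**Conclusion.** The concern holds in a limited form. The contradiction between Table 1 and sections 8.5/9.1 is plain in the text and affects which scans are taken. An SAP written later cannot restore scans that were not done. The best-response window in 9.5 has no end at new therapy, so the protocol's wording permits a response to a later drug to count in the go/no-go ORR if Table 1 is followed or unscheduled scans are used. With a threshold of 6 of 23, one such response can turn 5 into 6.

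The size cannot be fixed from the documents. Under the assumed ranges, the chance of passing at a true 13% moves from 4.6% to between 5.1% and 21.6%, with 9.3% at 20% switching and 15% response. If 8.5 and 9.1 are followed, ORR is not affected. The remaining issue is confined to deaths after a switch without recorded progression, which are PFS or DoR events dated at death. Those endpoints are secondary and carry no decision rule.

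This should be corrected before analysis, but it does not invalidate the design.

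**What to change.** 1. In section 9.5 (Overall response determination), end the best-response window at the earlier of progression/recurrence or the start of any new antineoplastic therapy.
2. Reconcile the Table 1 follow-up row with sections 8.5 and 9.1, so that one stopping event and one post-treatment imaging interval are stated throughout.
3. Keep the PFS and DoR definitions in section 9.4, and add a sensitivity analysis that censors at the last evaluable scan before new therapy.

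The cost is small: wording changes and one extra analysis. No new data are needed, because section 8.5 already records the start date of subsequent treatment. The downside is a possibly slightly lower ORR.
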